1.0 Objectives

In this multistep study, we will build on our prior efforts¹ to develop consensus on surveillance mammography and follow-up for breast cancer survivors who are age ≥ 75 by further developing expert-panel recommendations, examining clinician and patient attitudes towards these recommendations, and testing a strategy for communication of expert recommendations on mammography cessation through direct engagement of specialists, primary care clinicians (PCs), and patients. Specifically, we will work to reduce overscreening of older patients through the following aims:

- 1.1 Develop a communication tool that summarizes recommendations for clinicians and patients for surveillance mammography and follow-up care for breast cancer survivors age ≥ 75 . This will build off the work of a multidisciplinary expert panel which will come together for a meeting to develop draft recommendations (OHRS exempt protocol #18-526).
 - Interview up to 30 patients through telephone-based patient interviews and focus groups and interview oncologists and primary care providers (PCs) through 4-6 focus groups to learn their perceptions and thoughts about when to stop surveillance mammography, how to thoughtfully incorporate life expectancy into decision-making, how to communicate the benefits/risks of surveillance mammography, obtain feedback on the communication tool, and to explore optimal strategies for integrated and unified care between disciplines
 - Perform cognitive testing of the communication tool in up to 10 Dana-Farber breast cancer patients and further refine it for Aim 1.2
- 1.2 Test the surveillance mammography communication tool with older breast cancer survivors and their oncology clinicians
 - In a pre-post intervention study, examine the effect of the communication tool among 45 breast cancer survivors age ≥ 75 years (with low risk of in-breast recurrences) seen by oncologists on women's intentions for and knowledge of the pros and cons of surveillance mammography.

We hypothesize that our communication tool will lead to fewer women intending to receive surveillance mammography in the next year and women having more knowledge of the benefits and risks of surveillance mammography.

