****Baseline ('Pre') Patient Questionnaire****

Thank you for agreeing to participate in this study.

Study ID _____ (to be filled out by study team)

Date: _____

1. If your doctor or nurse asked you right now to make a choice about whether or not to get a mammogram, on a scale from 1-15 how certain are you about whether or not you would choose to get a mammogram in the next year? (1 means you are sure you would get a mammogram while 15 means you are sure you would not get a mammogram, if you are unsure please give a number between 1 to 15, 8 is the middle).

(If interview is being done over the phone because the in-person visit was missed, then ask patient: From 1-15, how likely are you to get a mammogram, 1 means you are certain I will get a mammogram and 15 means you are certain you will not get a mammogram. If you are not sure, please give a number between 1 and 15 that best describes how likely you are to get a mammogram)****

1	2	3	4	5	6	7	8	9	10	11	12	13	14	15
Will Get a Mammogram							Unsure				Will Not Get Mammogram			

As women age, the benefits of routine (when no symptoms are present) mammography may get smaller. As we try to learn from you, we would appreciate your honest answers to the questions below. These questions are about how you feel about whether or not to get a mammogram. Please say whether you Strongly Agree, Agree, are not sure, Disagree, or Strongly Disagree with the statements below.

2. I know which options are available to me for getting tested for breast cancer.

				
Strongly Agree	Agree	Not sure	Disagree	Strongly Disagree

3. I know the benefits of getting a mammogram.

				
Strongly Agree	Agree	Not sure	Disagree	Strongly Disagree

PROTOCOL TITLE:

4. I know the downsides or risks of getting a mammogram.

				
Strongly Agree	Agree	Not sure	Disagree	Strongly Disagree

5. I am clear about which benefits of getting a mammogram matter most to me.

				
Strongly Agree	Agree	Not sure	Disagree	Strongly Disagree

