The next set of questions are questions about mammograms in general. Your best guess is fine.

18. Among women aged 75 or older, who is more likely to die from breast cancer?

- Women who get mammograms
- Women who do NOT get mammograms
- There is almost no difference
- I don't know

19. The benefit of getting a mammogram is finding and treating a breast cancer when it is small and can be treated with only minor surgery.

- True False

20. Getting a mammogram will prevent me from getting breast cancer.

- True False

21. Most women who have an abnormal mammogram have breast cancer.

PROTOCOL TITLE:

- True False

22. Women aged 75 or older have a higher chance of getting breast cancer than younger women.

- True False

23. More women aged 75 or older die of heart disease than breast cancer.

- True False

24. Your other health problems should affect whether or not you get a mammogram.

- True False

25. Some breast cancers found by a mammogram would never have shown up or caused problems in a woman's lifetime. .

- True False

26. Most women aged 75 or older with breast cancer are treated with chemotherapy.

- True False

27. Some breast cancers are not detected by mammograms.

- True False

28. What is your preferred role in decision-making around mammography?

- I prefer to make the final decision about whether or not to get a mammogram.
- I prefer to make the final decision about whether or not to get a mammogram after seriously considering my health care provider's opinion.
- I prefer that my health care provider and I share responsibility for deciding whether or not to get a mammogram is best for me.
- I prefer that my health care provider make the final decision about whether or not I should get a mammogram, but seriously considers my opinion.
- I would prefer to leave all decisions regarding mammography to my health care provider.
- Don't know

We would like to get a sense of how much you worry about your cancer coming back. Please answer the next set of questions as honestly as possible.

29. On a scale of 1 – 6, with 6 being the most worried and 1 being the least worried, how much do you worry about your cancer coming back?

- | | | | | | |
|--------------------------|--------------------------|--------------------------|--------------------------|--------------------------|--------------------------|

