****Post-visit Patient Questionnaire****

Study ID: _____

Date: _____

Thank you for agreeing to participate in this study. Now that you have had your visit with your provider, there are a few more questions that we would like you to answer.

If your health care provider asked you right now to make a choice about whether or not to get a mammogram, on a scale from 1-15 how certain are you about whether or not you would choose to get a mammogram in the next

PROTOCOL TITLE:

year? (1 means you are sure you would get a mammogram while 15 means you are sure you would not get a mammogram, if you are unsure please give a number between 1 to 15, 8 is the middle).

1	2	3	4	5	6	7	8	9	10	11	12	13	14	15
Will Get a Mammogram					Unsure					Will Not Get Mammogram				

(**If interview is being done over the phone because the in-person visit was missed, then ask patient: From 1-15, how likely are you to get a mammogram, 1 means you are certain I will get a mammogram and 15 means you are certain you will not get a mammogram. If you are not sure, please give a number between 1 and 15 that best describes how likely you are to get a mammogram)**

2. When do you plan to get your next mammogram?

- Never
- In the next year
- More than 1 year from now but less than 2 years from now
- More than 2 years from now
- Other: _____

The next set of questions are about how you feel about whether or not to get a mammogram and are the same questions we asked you before your visit today. Please say whether you Strongly Agree, Agree, Neither, Disagree, or Strongly Disagree with the statements below.

3. I know which options are available to me for getting tested for breast cancer.

- | | | | | |
|--------------------------|--------------------------|--------------------------|--------------------------|--------------------------|
|  |  |  |  |  |
| Strongly Agree | Agree | Not sure | Disagree | Strongly Disagree |

4. I know the benefits of getting a mammogram.

- | | | | | |
|--------------------------|--------------------------|--------------------------|--------------------------|--------------------------|
|  |  |  |  |  |
| Strongly Agree | Agree | Not sure | Disagree | Strongly Disagree |

5. I know the downsides or risks of getting a mammogram.

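### The 'pre' questionnaire carries a hedged but directional statement about mammography between baseline intention and baseline conflict and knowledge; the post-visit form omits it, and a one-group design cannot separate its effect from the tool's

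*Protocol*

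**What the plan says.** Protocol section 1.0 describes Aim 1.2 as follows: "In a pre-post intervention study, examine the effect of the communication tool among 45 breast cancer survivors". There is no control group. The direction expected is explicit: "We hypothesize that our communication tool will lead to fewer women intending to receive surveillance mammography in the next year". Sections 8.4 and 8.5 make intention, on a 1-15 scale where higher means will not have a mammogram, a primary outcome alongside acceptability and feasibility.

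In Appendix D, item 1 of the 'pre' questionnaire asks "how certain are you about whether or not you would choose to get a mammogram in the next year". The text immediately after the item 1 scale reads "As women age, the benefits of routine (when no symptoms are present) mammography may get smaller". The 16 decisional-conflict items follow, beginning "I know which options are available to me for getting tested for breast cancer", and then the 10 knowledge items, introduced by "The next set of questions are questions about mammograms in general. Your best guess is fine".

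The post-visit questionnaire asks intention, conflict and knowledge again. It tells the woman that the conflict items "are the same questions we asked you before your visit today", but the sentence about benefits does not appear.

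The SAP names one inferential analysis, t-tests of the pre-to-post change in decisional conflict, intended to inform a future trial. It names no test of intention.

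**The concern.** A measuring instrument should not carry part of the message whose effect it is meant to measure. Here the statement comes after baseline intention is recorded and before post-visit intention. If it persuades anyone, it does so in the direction of the hypothesis, and the change is credited to the tool. With one group and two time points, no analysis can apportion the change.

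A second issue concerns the comparison that the SAP does test. Baseline conflict is answered directly after the statement; post-visit conflict is not. Several of the early conflict items ask whether she knows, and is clear about, the benefits and downsides of mammography, which is what the statement is about. The items match across forms, but the conditions under which they are answered do not.

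**Working it through.** This is mainly a check of order and wording. The plan gives no alpha, power, effect size or SD of change for the 45 women, so there is no stated figure to reproduce.

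**Step 1. The two forms side by side (Appendix D).**

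| Element | 'Pre' form | Post-visit form |
|---|---|---|
| Intention, 1-15 | Item 1, before the statement | First question |
| Statement on benefits and age | Between items 1 and 2 | Absent |
| Decisional conflict (16 items) | Items 2-17, directly after the statement | Items 3-18 |
| Knowledge (10 items) | Items 18-27, after the statement | Items 21-30 |

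The instruction before the conflict items also names the middle response differently (not sure on the 'pre' form, neither on the post form), although the printed options are the same.

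**Step 2. Direction of any effect.**
- Intention: for a woman who answers the form in order, the statement can affect only the post score. A message of lesser benefit would raise that score, which is the hypothesised direction.
- Conflict: the statement precedes the baseline. It might unsettle (higher baseline conflict, larger apparent fall) or inform (lower baseline conflict, smaller apparent fall). The documents do not settle which.
- Knowledge: the statement also precedes the baseline. An effect is possible but not shown.

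**Step 3. How sensitive the intention analysis is to a small shift (illustration only).** Assumptions not in the documents: two-sided 5% level, SD of the change score 2 to 4 points, no effect of the tool, and a shift from the statement alone of 0, 0.5 or 1 point. The paired-mean approximation to the chance of a significant result in the hypothesised direction is Φ(shift / (SD/√45) − 1.96).

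For example, with shift 0.5 and SD 3: 3/√45 = 0.447; 0.5/0.447 = 1.118; Φ(1.118 − 1.96) = Φ(−0.842) = 0.20.

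| Shift | SD 2 | SD 3 | SD 4 |
|---|---|---|---|
| 0 | 2.5% | 2.5% | 2.5% |
| 0.5 point | 39% | 20% | 13% |
| 1 point | 92% | 61% | 39% |

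A simulated signed-rank test on rounded differences, closer to the planned analysis, gives 35%, 19% and 14% for 0.5 point, and 90%, 57% and 35% for 1 point.

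**Step 4. The planned McNemar test.** If d women leave 'yes' and none enter it, the exact two-sided p is 2 × (1/2)^d. For d = 5, p = 0.0625; for d = 6, p = 0.031. Six women are 6/45 = 13.3% of the sample.

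Steps 3 and 4 show only that a sample of 45 can register a modest shift from any source. They do not estimate what the statement does.

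**The case against.** The strongest reply is that the statement adds little. It says benefits may get smaller, not that they do. The communication tool (Appendix B) says much the same at greater length, and section 5.3 has it shared together with the 'pre' survey, with no instruction to finish the survey first. A woman who reads the tool first brings a shifted baseline to item 1, which pulls the measured change towards zero. She could also read the statement before answering item 1, since no page break or lock is described. Other 'pre' items, such as those on other health problems and on cancers that would never cause trouble, could prompt reflection too. An uncontrolled change has many such sources, and the study is meant as preparation for a randomised one.

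Most of this stands as a limit on size. It does not remove the point. The statement is in a form that every participant is meant to complete, whereas section 5.3 leaves use of the tool in the visit to the clinician without specific instructions, and the clinician form allows for its not being used. In routine use the tool would come without this survey. Possible contamination of item 1 by the tool is a separate weakness and does not cure this one.

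A reader might go further and infer that item 18, "Among women aged 75 or older, who is more likely to die from breast cancer", is cued towards the answer of almost no difference, so that the knowledge gain is understated. The documents do not support that. They give no answer key, a benefit that may shrink is compatible with more than one answer, and item 18 is one of ten.

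**Conclusion.** The point holds as a possible, directional and inseparable influence on the intention outcome, and as a mismatch of lead-ins for decisional conflict. It rests on the printed order of the forms, the absence of a control group and the stated hypothesis.

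The size is unknown and may be small. A reader might infer that the survey does push intention, or might assign a share of the six switches in step 4 to the statement. Neither follows: no number of women moved can be taken from the documents, and the shifts in step 3 are assumptions. Nor does the mammography use of nearly 80% quoted in section 2.6 give a baseline for intention, since it is past-year use among survivors aged 65 or older in a national survey.

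For decisional conflict the direction of bias is uncertain; for baseline knowledge an effect is possible but not shown. Acceptability and feasibility are not affected by this argument. This is a modest point, worth acting on because the correction is almost free.

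**What to change.** Delete the statement from the 'pre' questionnaire and print the same neutral lead-in before the conflict items on both forms, saying only that the questions concern how she feels about having or not having a mammogram, with the same name for the middle response. Moving the statement to the end of the 'pre' form would protect baseline conflict and knowledge, but not post-visit intention; only deletion does that.

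The cost is a minor amendment to a draft survey, with no added patients, staff or data. The SAP is written in the past tense and section 7.1 anticipated completion by the end of 2020, so the forms may already have been used. In that case, state in the report that the pre-to-post changes in intention, conflict and knowledge include exposure to this sentence, and that the lead-in to the conflict items differed between forms. If the wording changes part-way, record which version each woman completed.

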****Post-visit Patient Questionnaire****

Study ID: _____

Date: _____

Thank you for agreeing to participate in this study. Now that you have had your visit with your provider, there are a few more questions that we would like you to answer.

If your health care provider asked you right now to make a choice about whether or not to get a mammogram, on a scale from 1-15 how certain are you about whether or not you would choose to get a mammogram in the next

PROTOCOL TITLE:

year? (1 means you are sure you would get a mammogram while 15 means you are sure you would not get a mammogram, if you are unsure please give a number between 1 to 15, 8 is the middle).

1	2	3	4	5	6	7	8	9	10	11	12	13	14	15
Will Get a Mammogram					Unsure					Will Not Get Mammogram				

(**If interview is being done over the phone because the in-person visit was missed, then ask patient: From 1-15, how likely are you to get a mammogram, 1 means you are certain I will get a mammogram and 15 means you are certain you will not get a mammogram. If you are not sure, please give a number between 1 and 15 that best describes how likely you are to get a mammogram)**

2. When do you plan to get your next mammogram?

- Never
- In the next year
- More than 1 year from now but less than 2 years from now
- More than 2 years from now
- Other: _____

The next set of questions are about how you feel about whether or not to get a mammogram and are the same questions we asked you before your visit today. Please say whether you Strongly Agree, Agree, Neither, Disagree, or Strongly Disagree with the statements below.

3. I know which options are available to me for getting tested for breast cancer.

- | | | | | |
|--------------------------|--------------------------|--------------------------|--------------------------|--------------------------|
|  |  |  |  |  |
| Strongly Agree | Agree | Not sure | Disagree | Strongly Disagree |

4. I know the benefits of getting a mammogram.

- | | | | | |
|--------------------------|--------------------------|--------------------------|--------------------------|--------------------------|
|  |  |  |  |  |
| Strongly Agree | Agree | Not sure | Disagree | Strongly Disagree |

5. I know the downsides or risks of getting a mammogram.

- | | | | | |
|--------------------------|--------------------------|--------------------------|--------------------------|--------------------------|
|  |  |  |  |  |
| Strongly Agree | Agree | Not sure | Disagree | Strongly Disagree |

6. I am clear about which benefits of getting a mammogram matter most to me.

- | | | | | |
|--------------------------|--------------------------|--------------------------|--------------------------|--------------------------|
|  |  |  |  |  |
| Strongly Agree | Agree | Not sure | Disagree | Strongly Disagree |

7. I am clear about which downsides or risks of getting a mammogram matter

PROTOCOL TITLE:

most to me.

				
Strongly Agree	Agree	Not sure	Disagree	Strongly Disagree

8. I am clear about whether the benefits of getting a mammogram are more important to me than the downsides or risks.

				
Strongly Agree	Agree	Not sure	Disagree	Strongly Disagree

9. I have enough support from others to make a choice whether or not to get a mammogram.

				
Strongly Agree	Agree	Not sure	Disagree	Strongly Disagree

10. I am choosing without pressure from others about whether or not to get a mammogram.

				
Strongly Agree	Agree	Not sure	Disagree	Strongly Disagree

11. I have enough advice to make a choice about whether or not to get a mammogram.

				
Strongly Agree	Agree	Not sure	Disagree	Strongly Disagree

12. I am clear about the best choice for me when it comes to getting mammograms

				
Strongly Agree	Agree	Not sure	Disagree	Strongly Disagree

13. I feel sure about what to choose in terms of whether or not to get a mammogram.

				
Strongly Agree	Agree	Not sure	Disagree	Strongly Disagree

14. The decision whether or not to get a mammogram is easy for me to make.

				
Strongly Agree	Agree	Not sure	Disagree	Strongly Disagree

15. I feel I have made an informed choice whether or not to get a mammogram.

				
Strongly Agree	Agree	Not sure	Disagree	Strongly Disagree

PROTOCOL TITLE:

16. My decision about whether or not to get a mammogram shows what is important to me

- | | | | | |
|--------------------------|--------------------------|--------------------------|--------------------------|--------------------------|
|  |  |  |  |  |
| Strongly
Agree | Agree | Not sure | Disagree | Strongly
Disagree |

17. I expect to stick with my decision whether or not to get a mammogram

- | | | | | |
|--------------------------|--------------------------|--------------------------|--------------------------|--------------------------|
|  |  |  |  |  |
| Strongly
Agree | Agree | Not sure | Disagree | Strongly
Disagree |

18. I am satisfied with my decision whether or not to get a mammogram.

- | | | | | |
|--------------------------|--------------------------|--------------------------|--------------------------|--------------------------|
|  |  |  |  |  |
| Strongly
Agree | Agree | Not sure | Disagree | Strongly
Disagree |

19. Did your health care provider discuss your life expectancy with you today?

- Yes
- No
- Don't know

20. If yes, how did this make you feel? You can check as many answers as you think apply:

- Comfortable
- Uncomfortable
- Informed
- Sad
- Content/Happy
- Scared
- Anxious
- Calm
- Interested
- Uninterested
- Other _____

The next questions are questions and are the same questions we asked you on your baseline survey. Please state whether each of the following statements is true or false (your best guess is fine).

21. Among women aged 75 or older, who is more likely to die from breast cancer?

- Women who get mammograms
- Women who do NOT get mammograms
- There is almost no difference
- Don't know

22. The benefit of getting a mammogram is finding and treating a breast cancer when it is small and can be treated with only minor surgery.

PROTOCOL TITLE:

- True False

23. Getting a mammogram will prevent me from getting breast cancer.

- True False

24. Most women who have an abnormal mammogram have breast cancer.

- True False

25. Women aged 75 or older have a higher chance of getting breast cancer than younger women.

- True False

26. More women aged 75 or older die of heart disease than breast cancer.

- True False

27. Your other health problems should affect whether or not you get a mammogram.

- True False

28. Some breast cancers found by a mammogram would never have shown up or caused problems in a woman's lifetime.

- True False

29. Most women aged 75 or older with breast cancer are treated with chemotherapy.

- True False

30. Some breast cancers are not detected by mammograms.

- True False

The next questions are about the communication tool that we provided you before your clinic visit

Did it...

31. Help you recognize that a decision needs to be made about whether or not to get a mammogram?

- A great deal Quite a bit Somewhat A little Not at all

32. Prepare you to make a better decision about whether or not to get a mammogram?

- A great deal Quite a bit Somewhat A little Not at all

33. Help you think about the pros and cons of getting a mammogram?

- A great deal Quite a bit Somewhat A little Not at all

34. Help you think about which pros and cons about getting a mammogram are most important to you?

- A great deal Quite a bit Somewhat A little Not at all

PROTOCOL TITLE:

35. Help you know that the decision whether or not to get a mammogram depends on what matters most to you?

-
- A great deal Quite a bit Somewhat A little Not at all

36. Help you organize your own thoughts about the decision whether or not to get a mammogram?

-
- A great deal Quite a bit Somewhat A little Not at all

37. Help you think about how involved you want to be in this decision?

-
- A great deal Quite a bit Somewhat A little Not at all

38. Help you identify questions you want to ask your health care provider about mammography?

-
- A great deal Quite a bit Somewhat A little Not at all

39. Prepare you to talk to your health care provider about what matters most to you about whether or not to get a mammogram?

-
- A great deal Quite a bit Somewhat A little Not at all

40. Prepare you for a follow-up visit with your doctor?

-
- A great deal Quite a bit Somewhat A little Not at all

41. At your follow-up visit, did you talk to your health care provider about getting a mammogram?

- YES NO

42. Did your provider talk to you about the benefits of getting a mammogram?

- YES NO

43. Did your provider talk to you about any downsides of getting a mammogram?

- YES NO

44. What did your provider recommend in terms of mammograms?

- Continue having mammograms
- Get another mammogram but consider stopping after that
- It is my choice
- To not get a mammogram now but reconsider later
- To stop getting mammograms
- Other: _____

45. The length of the communication sheet was

-

PROTOCOL TITLE:

- | | | | | |
|---------------|-------------------|------------|--------------------|----------------|
| Much too Long | A little too long | Just right | A little too short | Much too short |
|---------------|-------------------|------------|--------------------|----------------|
46. The amount of information was
- | | | | | |
|--|--|-------------------------------------|--|--|
|  Much less than needed |  A little less than needed |  Just right |  A little more than needed |  Much more than needed |
|--|--|-------------------------------------|--|--|
47. How clear was the information?
- | | | | |
|---|---|---|---|
|  Everything was clear |  Most things were clear |  Some things were clear |  Many things were unclear |
|---|---|---|---|
48. I found the information
- | | | | | |
|--|---|--|---|--|
|  Clearly slanted towards getting a mammogram |  A little slanted towards getting a mammogram |  Completely balanced |  A little slanted towards NOT getting a mammogram |  Clearly slanted towards NOT getting mammogram |
|--|---|--|---|--|
49. Reading the information made me feel:
- | | | | |
|---|---|---------------------------------------|---|
|  Not anxious at all |  A little anxious |  Very anxious |  As anxious as could be |
|---|---|---------------------------------------|---|
50. Please check the most accurate statement below:
- I understood none of the information
 - I understood a little of the information
 - I understood most of the information
 - I fully understood all of the information

Any other Comments for us??

51. How helpful was the communication tool in making a decision about mammography?
- | | | | |
|---------------------------------------|---|---|--------------------------------------|
|  Very helpful |  Somewhat helpful |  A little helpful |  Not helpful |
|---------------------------------------|---|---|--------------------------------------|
52. Would you recommend the use of this communication tool?
- | | | | |
|---|---|---|---|
|  Definitely Recommend |  Probably Recommend |  Probably not Recommend |  Definitely not Recommend |
|---|---|---|---|

PROTOCOL TITLE:

It would be helpful to learn how you prefer to receive health educational materials such as the one you read today.

53. What is your preferred format for health education materials:

- A pamphlet like the one you read for this study
- The computer/internet
- No preference
- Other

54. Which would you prefer:

- To be mailed health educational materials that relate to me before a visit
- To be emailed health educational materials that relate to me before a visit
- To receive health educational materials in the waiting room before a visit
- To have your doctor or nurse give you health educational materials during the visit
- To have your doctor's staff give you health educational materials after a visit to read at home.
- No preference
- Other

Thank you so much for your help. You will receive \$40 for participating in this study.

PROTOCOL TITLE:

